## **5.0 STUDY PROCEDURES**

### **5.1 Enrollment Procedures**

For the primary objective, eligible participants (as identified by screener) will be contacted by email and/or phone, and invited to the SRV in their city. Once at the SRV, study staff will consent the participants, randomize the participants, and then provide a computer for the participants to complete the baseline survey. Once they have consented, participants will be considered formally enrolled in the study. After completion of the baseline survey, study staff will assist participants with accessing the WebApp, creating a strong but memorable password, and bookmarking the WebApp (if participants choose to). If more than 30 days occurs between screening and the baseline visit, eligibility will be re-determined at the baseline visit.

For the secondary objective, eligible participants (as identified by screener) will be contacted by the study team to schedule an interview. If the individual is deemed capable and willing, they will be consented by a member of the study team.

For the tertiary objective, eligible participants will be contacted by calling the site or the site director directly (if contact information is available) to schedule an interview.

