- ATOD (alcohol, tobacco, and other drug) use:* We will assess frequency of ATOD use (as measured in NSDUH) over the past 30 days (3 months in 3-, 6-, 9-, and 12-month follow-up surveys) for alcohol, tobacco products, cannabis, cocaine, amphetamine type stimulants, inhalants, sedatives or sleeping pills, hallucinogens, and opioids. We will also ask age of onset. If respondents indicate alcohol use, we will ask the Alcohol Use Disorders Identification Test (AUDIT) developed by the WHO (World Health Organization). AUDIT is a 10-item screening questionnaire with 3 questions on the amount and frequency of drinking, 3 questions on alcohol dependence, and 4 on problems caused by alcohol.
- Psychological Distress:* We will measure this using existing, well-validated scales. We will use subscales from the Brief Symptom Inventory to measure depressive symptoms and anxiety symptoms. Depressive symptoms include 6 items rated on a 5-point scale (1=never, 5=very often). Items include feelings of loneliness, blue or sad, and having

thoughts of ending one's life. Anxiety also includes 6 items measured on the same 5-point scale and includes reporting nervousness or shakiness, feeling fearful, or suddenly scared for no reason. We will use the 10-item Rosenberg Self-Esteem^66, measured on 4-points (0=Strongly disagree-3=Strongly agree).

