#### 7.3.2. Mystery Shopper Data

For the second objective, mystery shopper participants will video chat, audio chat, or chat in-person with a study team member about every site visit, following the visit(s). If a video chat occurs, the BlueJeans platform will be used. These conversations are designed to give mystery shoppers an opportunity to discuss and process their visit and any notable incidents at a point when the visit is very recent and easily memorable. If any troublesome or adverse events are reported to the study team member, the study team member can provide the participant with support and external services, in addition to documenting the incident.

After each visit, Mystery Shoppers will complete a brief evaluation of the site using a web-based CASI at the SRV. All survey data will be collected using Qualtrics. Data will remain confidential; no personal identifying information will be collected during the computer session. The participant's unique SID# will be used in order to link the interview responses to the participant's CRF data. We will download the data directly from the administrative web application interface and manage it using Microsoft Excel. The data collected will be stored in a database held within a University of Pennsylvania secure server.

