### **8.3 Intervening on "Social Harms"**

All sites have specific policies governing the treatment of human participants. These policies specify that medical and psychological assistance will be available in the immediate environment in the event a participant should experience any adverse reactions resulting from study procedures.

While participants will be informed that they may refuse to answer any question at any time, responses or reactions to certain questions may indicate distress on the part of the participants. If at any time during the study, a participant divulges that he is at risk for harm, including but not limited to being abused or experiencing violence, if harm is suspected or likely, or if the participant states he is suicidal/homicidal, measures will be taken to ensure his or her safety. Reporting will be done as appropriate to the situation and the legal statutes, including reporting

to child protection agencies or other appropriate agencies and referrals will be provided to appropriate support, counseling, or treatment resources.

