## 11.3 Risks and Benefits

### 11.3.1 Risks

Some participants may be uncomfortable answering questions about their past sexual behavior and HIV-related behaviors. All information used in enrollment and recruitment describing the research activities will include a detailed description of the content and expected participation of the respondent, such that the respondent is aware of the nature of the questions and topics to be discussed. Respondents will complete their surveys online to maximize convenience and privacy. Informed consent documents will inform research participants of their rights as participants. During the consent process, participants will be reminded that they are free to refuse to participate in any study activities or choose to terminate their participation at any time. Our consent forms will also include information on limits of confidentiality (e.g., suicidal intent, homicidal intent, child abuse, etc.) and mandatory reporting requirements, which will be reviewed by all participants. While our surveys do not directly ask participants about child abuse or harm to others, it is possible that participants may volunteer this information. In such occurrences, we will follow established protocols used in our prior studies to assess risk level and follow-up appropriately.

Participants will provide their names and addresses or other personally identifying information as part of the study. There is a risk that these data could be unintentionally disclosed to someone not authorized to access the data, compromising the privacy of the participant. To reduce this risk, all contact information for the study participants will be kept in a password-protected location, with access restricted to the Study Coordinators and PIs.

Although we are not directly providing HIV testing, we are providing information on where participants can test for HIV in their locale. Participants who learn that they are HIV-positive or STI sero-positive may be distressed to learn of their health condition. This poses the greatest emotional and physical risk to participants in the research study. Given that our intervention seeks to link YMSM to HIV/STI testing locations, risks of distress are minimized by encouraging YMSM to receive their results at an agency that may offer counseling and referrals.

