To minimize the risk of participants feeling uncomfortable about answering personal questions, we will use Computer Assisted Self Interview (CASI) methods for the study's surveys. In a CASI, participants read survey questions on a computer or mobile phone and use a combination of mouse click and keyboard/touchscreen entry to input the answers themselves. Participants will also be able to refuse to answer most questions that make them uncomfortable.

For mystery shoppers who evaluate testing sites, the potential risk will be minimal. There is a risk of untoward events occurring during sessions that may personally affect them. Training and guidance will seek to minimize this risk. Additionally, a post-visit debriefing session with a member of the study team will help ensure any untoward events are discussed and resources are offered that may assist the mystery shopper.

For agency directors who participate in qualitative interviews, the potential risk will be minimal. There is a risk of violation of confidentiality and potential distress when discussing HIV/STI-related issues, but agency directors will be informed of the confidential nature of the research. These interviews will occur via a secure, encrypted teleconference interface (BlueJeans) to maximize security and privacy. We will remove all identifying information from quotes (agency names, etc.) and if quotes clearly identify an agency, they will not be included in the

presentations of results.

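### The RCT baseline survey asks about suicidal thoughts, but no step in the document makes a positive answer known to site staff

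*Combined protocol and SAP*

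**What the plan says.** **The item.** Section 6.1.1, under Psychological Distress, lists a six-item depressive-symptom subscale scored 1 (never) to 5 (very often). It includes "thoughts of ending one's life".

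**Who answers it.** Participants aged 15 to 24 (section 4.1). Section 4.8 says a waiver of parental consent will be requested for those aged 15 to 17.

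**How it is answered.** Baseline takes place at the SRV. Staff log the participant in (Study Abstract, Data Collection). Participants then "use a combination of mouse click and keyboard/touchscreen entry to input the answers themselves" (section 11.3.1).

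**What follows.** "After completion of the baseline survey, study staff will assist participants with accessing the WebApp" (section 5.1), along with choosing a password and, if wanted, bookmarking the site. Answers are sent to the Analytic Core and downloaded there routinely (sections 7.3.4 and 7.4.3).

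**What protects a distressed participant.** Section 8.3 recognises that "responses or reactions to certain questions may indicate distress on the part of the participants". It requires action if a participant divulges risk, if harm is suspected, or if he states that he is suicidal, and it says psychological help will be close at hand. Section 4.8 requires each participant, before enrolment, to explain what he would do if distressed. Section 8.4 offers a referral list on the study website and a contact route to staff. Section 9.0 requires psychological distress to be reported. Section 11.3.1 says the consent forms name suicidal intent among the limits of confidentiality.

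**The concern.** The trial itself puts this question to adolescents and young adults, so it should be able to say what happens when someone answers it high. The document describes what staff must do once they know of a risk. It does not describe how they come to know of one that exists only as a selected response on a screen.

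The missed opportunity is specific. At baseline the participant is on site, staff are present, and section 8.3 places psychological help nearby. Followed as written, the plan lets a participant select the highest frequency, say nothing, receive help with his WebApp account and leave. No action is triggered at the moment when acting would be easiest.

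**Working it through.** This is a question of procedure, so the check is to follow one silent high answer through every relevant section and ask whether any step brings it to SRV staff.

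| Section | What it does | Does it detect a silent answer? |
|---|---|---|
| Study Abstract; 11.3.1 (computer self-interview) | Staff log the participant in; he enters the answers | No. Being present does not show staff the response |
| 5.1 | Staff go from survey completion to WebApp set-up | No. No review of answers is listed |
| 7.3.4, 7.4.3 | Encrypted transfer to the Analytic Core, routine download | No. No alert back to the site is described |
| 7.2, 7.3.3 | Survey data carry a study ID; names are kept apart in the retention system | No. An analyst who saw the score would have to link it back, and no such step is written |
| 8.3 | Duty to act when risk is divulged, stated or suspected | No. It sets no score, reader or time for this item |
| 4.8 | Participant explains what he would do if distressed | No. It prepares him to seek help himself |
| 8.4 | Referral list and contact route | No. He must use them himself |
| 9.0 | Reporting of effects apparent to staff or later reported to them | No. A silent answer is neither |
| 11.3.1 (consent and risk protocols) | Consent forms name suicidal intent; established risk protocols are mentioned | No. The protocols follow the sentence beginning "While our surveys do not directly ask participants about child abuse or harm to others" and concern what participants volunteer |

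**Reading section 8.3 broadly.** Its reference to responses can be taken to include a survey answer. That settles that a duty would exist, but not how anyone learns that it has arisen.

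**Follow-up.** Section 5.4.1 says the later surveys repeat many, not all, of the baseline questions and can be done online. The item is therefore confirmed at baseline only.

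**Size.** Planned enrolment is 480 over three cities, and 480 / 3 = 160 per SRV, as the Study Abstract states. With one baseline survey each, there are at most 480 answers. This is a ceiling for two reasons: enrolment counts from consent, before the survey (section 5.1), and "Participants will also be able to refuse to answer most questions that make them uncomfortable" (section 11.3.1). The documents give neither an endorsement rate nor a trigger score. If a share p reached the trigger, the count would be at most 480 × p. For assumed values of 0.5%, 1% and 5% that is 2.4, 4.8 and 24. These values only illustrate the formula.

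**The case against.** **A rule may exist outside the file.** Section 8.3 refers to site policies, section 9.0 to IRB procedures and staff training, section 5.4.5 to a central research protocol still to be developed, and section 11.3.1 to a Data and Safety Monitoring Plan. The consent forms, which section 11.3.1 says cover suicidal intent, were removed before review. This stands: an absent rule cannot be told from an unseen one. But sections 5.1 and 6.1.1 point to none of these sources for this item, so a site working from the protocol would not know where to look.

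**The plan is not silent on suicidality.** A reader might infer that it overlooked the subject. The documents do not support that. Section 8.3 names it, the consent forms name it, and section 4.8 tests each participant, minors included, on what he would do if distressed. These are real safeguards. What is missing is the link between the answer and the duty.

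**Mystery shoppers are not a precedent.** Shoppers are told that "a post-visit debriefing session with a member of the study team will help ensure any untoward events are discussed and resources are offered" (section 11.3.1), and a reader might infer that RCT participants were denied an equivalent check. That debrief deals with events at testing sites, not with questionnaire answers about mood, so it shows nothing about how a survey item should be screened.

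**The item is not a risk screen.** It is one of six frequency-rated items, and the text gives no recall period for it. A reader might compute that at least one trigger answer is nearly certain: at an assumed 0.5%, 1 − 0.995^480 = 0.91, and at 1%, 1 − 0.99^480 = 0.99. Those figures rest on assumed rates, independent answers, all 480 answering and a cut-off nobody has defined. They measure neither imminent risk nor harm, and the point does not depend on them.

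**Conclusion.** The point holds as a gap in detection. The document contains a duty to respond and several routes that depend on the participant speaking up or staff noticing distress. It contains no step that makes a high answer to this baseline item known to SRV staff. This is more than missing detail, because following the text as written leaves a silent high answer without any action while help is on the premises.

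The number of participants affected cannot be sized from the documents, beyond the ceiling of 480 baseline answers. The conclusion assumes that no rule in the unseen sources already covers the item. If one does, the defect shrinks to a missing cross-reference. Confidence is therefore moderate. The change should be made, and it touches no primary analysis.

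**What to change.** **If a rule already exists**, cite it in sections 5.1 and 8.3. That is a sentence in each place.

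**Otherwise:**

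- (a) Program the survey so that any answer above never on this item shows the section 8.4 referral list on screen, with a crisis line included. The survey already branches on an answer: the alcohol questionnaire appears only if use is reported (section 6.1.1).
- (b) Have the study's clinical lead set a trigger score in advance. Add to section 5.1 that SRV staff check a flag for this item before the participant leaves and, if it is positive, start the section 8.3 procedure. One workable form is a neutral code on the survey's closing page, read before WebApp set-up. It needs no feed back from the Analytic Core and shows staff a flag rather than his answers, in keeping with the role-based access in section 11.3.1.
- (c) State whether the item recurs at follow-up. If it does, use the same on-screen display in the online surveys.

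**Cost.** Minor survey programming, an IRB modification (section 11.4), possibly a consent line saying that this answer is flagged, and a little time from existing SRV staff. The main downside is that some participants may under-report once they know the item is flagged, which works against the comfort that self-interviewing is meant to give. Psychological distress is a covariate and possible moderator (section 10.1.1), not a primary outcome, and the rule would be the same in both arms.

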### 6.1.2 On-study Evaluations/Measures

- *HIV Testing:* Follow-up surveys will repeat the HIV testing questions in each follow-up survey. The HIV testing outcome will be: the proportion of MSM tested for HIV two or more times at least 3 months apart in the 12-month follow-up period (“frequent tester”). As an additional analysis, we will also examine the proportions of participants who receive one HIV test.
  - Among self-reported newly diagnosed HIV+ cases, we will measure their linkage and engagement with appropriate medical care after initial diagnosis using criteria employed in prior ATN protocols with youth. We will define linkage as an HIV-related medical visit within 45 days of referral, and engagement as a second HIV-related medical visit within 16 weeks of initial visit. Onset of ART initiation, self-reported adherence to ART, and viral suppression are exploratory indicators, as we recognize that our follow-up period may not be a sufficient amount of time to see these changes.
- *STI Testing:* The STI testing outcome is defined as the proportion of YMSM tested for STIs at least once in the 12-month follow-up period. We will ask participants what STIs they have been tested for, the anatomic sites where they were tested, the date of their most recent STI test (if known), and whether a medical provider had diagnosed them with an STI. In the follow-up surveys, we will ask participants whether they had been tested for STIs in the past 3 months (for the 1-month follow-up survey, we ask about the past 30 days). If STI testing is reported, we will ask participants to indicate what tests they received, and whether they were diagnosed with an STI by a medical provider.
- *PrEP Use:* At each follow-up assessment, PrEP-eligible HIV-negative YMSM (per CDC guidelines) will be asked whether they have begun using PrEP. We will also ascertain if a provider recommended PrEP and/or were offered a prescription for PrEP.
 

*Site Evaluations:* Across both trial arms, YMSM who report testing in the prior 3 months will complete self-evaluation forms of their testing experiences to assess comfort, quality, and concerns after visiting a site for HIV/STI testing and PrEP prevention services. The assessment form is the same form used by the mystery shoppers. We will use these data to update the WebApp and to send aggregate data of YMSM's satisfaction with services to agencies biannually.
- *Intervention Acceptability:* At each follow-up, YMSM will report data on the acceptability of their assigned arm. We will also use the Systems Usability Scale to ascertain participants' overall satisfaction with the intervention, perception of the information quality, and perceived usefulness of their intervention to improve their health.
- *Use of Intervention over time:* We will measure intervention exposure using paradata

(e.g., process data emerging from use of the WebApp) from backend database of the intervention website, including counts of user sessions, session lengths, pages visited, and functions utilized. This information will assist in examining whether intervention dosage influences the overall efficacy of the intervention, and inform the cost analysis and wider implementation and scalability.

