### **Binary outcomes such as HIV testing:**

The percentage of participants who report routine HIV testing over a 12-month period will be compared between the intervention arms (GC and the Control condition). Five assessments will occur at 1 month (visit window  $\pm$  1 month), 3 months ( $\pm$  1 month), 6 months ( $\pm$  1 month), 9 months ( $\pm$  1 month), and 12 months ( $\pm$  1 month). Repeated-measures analyses for HIV testing will be implemented by performing a generalized estimating equations (GEE) analysis via the SAS GENMOD Procedure (version 9.4; SAS Institute, Cary, NC) with an exchangeable correlation structure for the repeated measures within participant (binomial-logit model). The statistical model will include three predictors (intervention arm, time on study and the statistical interaction between intervention arm and time on study). The statistical model will provide estimates of the percentages of participants reporting HIV testing (plus 95% confidence intervals) by intervention arm and time on study. The model-based estimates are unbiased with unbalanced and missing data, so long as the missing data are non-informative (missing completely at random, MCAR). A P value  $\leq 0.05$  will be considered statistically significant for the main effects (intervention and time on study) and for the intervention by time on study interaction effect from the repeated measures analysis. **The statistical test for interaction between time on study and intervention arm will be the primary overall hypothesis test to determine whether HIV testing in the intervention groups changed in significantly different ways during follow-up (i.e., different temporal patterns over time).** If HIV testing rates in the two intervention groups are consistently different or similar (i.e., no statistical interaction) then the main effect test for intervention will be used as the primary test of intervention efficacy. If a significant interaction is detected, then Wald chi-square tests will be used to compare the differences between the model-based HIV testing estimates at each time interval and to compare differences over time within each intervention arm. Specific statistical tests will be done within the framework of the generalized linear model. All statistical tests will be 2-sided and unadjusted for multiple comparisons.

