The primary assessment for a difference between intervention arms for 'frequent tester' rates will be a two-sided Z-test for independent proportions with pooled variance. Confidence intervals (95%) will also be reported for the observed difference between the GC and control arms in 'frequent tester' rates. The same analysis plan described above will be used for the other primary outcomes that as binary (i.e., STI testing, PrEP awareness).

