profile (e.g., socio-demographics, HIV/STI testing history and testing motivations, recent sexual behavior, sources of support, self-reported values), as reported by participants' answers to their baseline assessment. At the individual-level, GC delivers tailored online content specific to each user's demographic characteristics (e.g., age, race/ethnicity, location, relationship status), HIV/STI risk behaviors (e.g., HIV/STI testing history; substance use; communication with partners regarding status) and sociocultural context (e.g., homelessness, incarceration). GC also employs tailoring at the systems-level. Participants across both conditions who report being tested since their last follow-up survey will be asked to complete a site assessment as part of their follow-up survey. Testing sites will receive biannual performance summaries that include aggregated participant scores from the site assessments, qualitative feedback participants provided, and their sites' scores in relation to other testing sites in their city. These summaries are provided in an effort to help sites understand their performance based on quality assurance evaluations from YMSM clients and to optimize service delivery if needed. The study team and Analytic Core will ensure that these summaries will not include any identifying information about participants.

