## 5.4 Intervention/Investigation Procedures

### 5.4.1 Get Connected Intervention

Participants will complete a 30- to 45-minute baseline survey that includes questions on lifetime HIV testing history, lifetime STI testing history and knowledge about STIs, date of their most recent STI test (if known), and whether they were ever diagnosed with an STI. GC will use baseline survey data to select and deliver personalized, tailored content to YMSM assigned to the intervention. Furthermore, as part of the participant's baseline visit, study staff will collect contact information where participants may be reached for follow-up assessments. We will use best practices to retain participants (e.g., collecting participant's cell phone number, email address, Facebook, WhatsApp, and/or Skype username, and contact information for 2 peers who could help us contact them). Additional surveys will occur at 1, 3, 6, 9, and 12 months after intervention initiation, and can be completed online. These follow-up surveys will repeat many of the questions from the baseline survey and will also include additional questions on HIV and STI testing in each 3-month period, including test results. These surveys will be the same for participants in the control and intervention arms. For participants in the intervention arm, the GC WebApp will be retailored after each follow-up survey, based on any different information provided on key questions.

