## 10.3 Statistical Analysis Plan

10.3.1 We will use the general framework of generalized linear mixed models (GLMM) to test for intervention effects over time. Note that some of our outcomes are binary, some count and some continuous traits, and thus need to be treated differently. The general form of the GLMM will be  $g(\mu_{ij}) = \beta_0 i + \beta_{cov} Covariates_{ij} + \beta_{Time} j + \beta_{Trt} Trt_{Armi} + \beta_{Arm \times Time}$ , where  $\beta$  is the mean response corresponding to subject  $i$  at Time  $j$  (baseline and 4 follow-ups), with its appropriate link function (identity for continuous outcome, logit for binary outcome and natural log for count outcomes);  $Trt = 1$  if the  $i$ -th subject is in the intervention group and 0 if the  $i$ -th subject is in the attention-control group. The interaction coefficients are of interest here, measuring the difference in the rate of change in outcome across the two treatment groups over time. The subject-specific random intercepts are assumed to be normally distributed with a common variance and they account for within-person correlation. We will also explore if we need a subject-specific random-slope corresponding to visit in the above model. Maximum likelihood estimation will be used for fixed effect parameters. Models will be compared according to information criterion like AIC, BIC. For some binary outcomes like HIV testing, we will perform an aggregate analysis after collapsing across the repeated measures using simple logistic regression comparing whether the probability of having tested at least once over the entire FU period is different across treatment groups, after adjusting for baseline values. To ensure robustness, we will also apply an exchangeable working correlation structure to its corresponding generalized estimating equation (GEE) model. We will also conduct exploratory regression analyses to examine city differences in the outcomes. These regressions will be run with group assignment and city in the model, controlling for socio-demographic characteristics.

Interactions between group assignment and city will be tested to explore potential site-specific moderators of treatment effect.

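### The STI testing GEE pools a 30-day report at month 1 with 3-month reports later, so its time effect is an artefact and its averaged arm effect leans towards early response

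*Combined protocol and SAP*

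**What the plan says.** Section 6.1.2 sets the STI recall window. Follow-up surveys ask "whether they had been tested for STIs in the past 3 months (for the 1-month follow-up survey, we ask about the past 30 days").

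Section 2.4 (binary outcomes) specifies a binomial-logit GEE with exchangeable correlation over surveys at months 1, 3, 6, 9 and 12, each with a window of ±1 month. Arm, time and arm by time are each tested at P ≤ 0.05. The interaction is the primary overall test, and the arm main effect takes over if there is no interaction. For HIV testing, "The statistical model will provide estimates of the percentages of participants reporting HIV testing" by arm and time. The plan then extends to STI testing: "The same analysis plan described above will be used for the other primary outcomes that as binary (i.e., STI testing, PrEP awareness"). Nothing in it adjusts for window length or overlap.

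For HIV testing no window is given survey by survey. Section 6.1.2 says "Follow-up surveys will repeat the HIV testing questions in each follow-up survey". Section 5.4.1 mentions "additional questions on HIV and STI testing in each 3-month period, including test results". Section 3.1, describing who completes a site assessment, uses another interval: "Participants across both conditions who report being tested since their last follow-up survey will be asked to complete a site assessment".

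Section 10.3.1 describes a GLMM with baseline and four follow-ups, although five are scheduled. Its interaction coefficients are described as "measuring the difference in the rate of change in outcome across the two treatment groups over time". The baseline survey collects "lifetime HIV testing history, lifetime STI testing history and knowledge about STIs" (Section 5.4.1), plus the date of the last STI test if known.

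**The concern.** A model of one binary outcome at five times needs the outcome to mean the same thing each time. Here month 1 records any STI test in 30 days, and every later visit records any test in 3 months. The month-1 percentage is therefore lower by construction, and the time effect partly measures the questionnaire. The hypothesis concerns increases in testing, so a rise after month 1 invites misreading.

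The second issue is overlap. A man tested in the first month can be positive at both month 1 and month 3, so early testing gets extra weight in the arm effect averaged over visits. The stated interest is testing over 12 months, while the pilot evidence in Section 1.2.3 stops at 30 days. How an early effect is weighted against a sustained or late one therefore matters.

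**Working it through.** **Inputs from the documents.** Recall windows (6.1.2); survey times, ±1 month windows and model terms (2.4); month-3 notice sent 2 months after the month-1 survey (8.1); 400 participants analysed (10.2).

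**Assumptions.** The documents give no STI testing rate, so rates are varied. The simulations use 200 men per arm, complete data, a gamma frailty of variance 1 for differences between men, and robust Wald tests in the saturated arm-by-time logit model.

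**1. The plan's own figure.** Section 10.2 requires 400 for an absolute difference of 13 points. With pooled variance, two-sided 0.05 and 80% power, 25% versus 38% needs 200 per arm, or 400. The control rate of 25% is inferred. The calculation uses one proportion per man, so recall windows do not enter it.

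**2. Window length alone.** At a constant rate, p(30 days) = 1 − (1 − p3)^(1/3).

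| 3-month % | 30-day % | Odds ratio, 3 months vs 30 days |
|---|---|---|
| 15 | 5.3 | 3.17 |
| 20 | 7.2 | 3.24 |
| 30 | 11.2 | 3.39 |
| 40 | 15.7 | 3.59 |
| 50 | 20.6 | 3.85 |

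Absolute arm differences are distorted too. With 20% per 3 months and a constant hazard ratio of 1.5, the later difference is (1 − 0.8^1.5) − 0.20 = 8.4 points. At month 1 it is (1 − 0.8^0.5) − 0.072 = 3.4 points.

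**3. Rejection rates with no arm effect and no change in behaviour.**

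| Test | 20% per 3 months | 26.5% per 3 months |
|---|---|---|
| Time, all five visits | 100% | 100% |
| Time, months 3–12 only | 4.7% | 4.6% |
| Arm | 4.5% | 5.1% |
| Arm by time | 4.9% | 4.9% |

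**4. Overlap.** For surveys completed at months t1 and t3, overlap = max(0, min(t1, t3) − max(t1 − 1, t3 − 3)).
- t1 = 1, t3 = 3: 1 − 0 = 1 month, the whole month-1 window.
- t1 = 1, t3 = 4: 1 − 1 = 0.
- t1 = 2, t3 = 4: 2 − 1 = 1 month.

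A month-3 survey completed at month 2 reaches back one month before baseline.

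**5. Weighting of the arm effect.** Take 0.12 tests per month. With frailty variance 1, the odds of any test in a window equal the expected number of tests in it: 0.12 for 30 days, 0.36 for 3 months (26.5%). The mean log odds ratio over visits then follows directly.
- Constant rate ratio 1.5: ln 1.5 = 0.41 at every visit, with or without month 1.
- Rate ratio 3 in month 1 only: ln(0.36/0.12) = 1.10 at month 1, ln(0.60/0.36) = 0.51 at month 3, then 0. Five visits: 1.61/5 = 0.32. Non-overlapping windows (0–1, 1–3, then quarterly): 1.10/5 = 0.22. Four equal windows: 0.51/4 = 0.13.
- Rate ratio 1.5 after month 3 only: 3 × 0.405/5 = 0.24 with five visits; 3 × 0.405/4 = 0.30 with four.

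| Effect (26.5% per 3 months) | Arm test rejects, five visits | Months 3–12 only |
|---|---|---|
| Constant, 1.5 | 77% | 82% |
| Month 1 only, 3 | 58% | 15% |
| After month 3, 1.5 | 37% | 58% |

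At 20% per 3 months, the constant effect gives 71% and 77%, and the late effect 31% and 51%.

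**6. The interaction gate.** The arm test is primary only when the interaction is not significant. For an effect confined to month 1 (20% per 3 months, rate ratio 2.5), the interaction rejects in 57% of trials. In two separate simulations the arm test rejects in 37% and 38% ungated, but is both reached and significant in only 11% and 14%.

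**The case against.** The main counter-argument is that efficacy rests on arm by time, then arm, and both arms answer the same questions over the same windows. That stands: neither test gains false positives, and a constant effect is estimated correctly on the odds-ratio scale. Within-arm comparisons over time are planned only after a significant interaction. The interaction gate also catches many effects confined to the first month, and the 58% and 15% above are rejection rates under a real effect, not error rates.

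Nor is the four-visit log odds ratio the truth against which the five-visit value is wrong. In the early-only case overlap accounts for 0.32/0.22, about 1.46-fold; the rest comes from leaving month 1 out. The month-1-only effect is itself an assumption, and Section 5.4.1 says content is re-tailored after each follow-up.

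Three stronger readings are tempting but unsupported.
- A reader might infer that HIV testing, the trial's primary outcome, has the same defect. The 30-day window is documented for STI testing only, and Sections 5.4.1 and 3.1 point to different intervals.
- A reader might infer that Section 10.3 uses lifetime history as the time-0 response. It does not say how baseline is coded. A recent-window value could be derived for STI from the last test date, and the four follow-ups may already omit month 1.
- A reader might infer that every month-1 test is counted again at month 3. That holds at nominal times only; late completion of month 3 can remove the overlap.

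**Conclusion.** The point holds for the STI testing GEE in Section 2.4. Its time test, run at 0.05, rejects in about 100% of trials when behaviour is constant, and the month-1 percentage cannot be compared with later ones. Only contrasts with month 1 are affected; months 3, 6, 9 and 12 have equal windows. The visit-averaged arm effect is weighted towards early response: larger for an effect that fades, and smaller with less power for one that starts late. These sizes rest on the assumed rates, frailty and complete data. The window-length odds ratio of 3.2 to 3.9 holds for constant rates of 15% to 50% per 3 months.

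The endpoint of at least one STI test in 12 months, the frequent-tester Z-test, the collapsed logistic regression and the basis for 400 use one value per man and are unaffected. For HIV testing the finding is a missing definition: 30 days at month 1 would repeat the problem, and 3 months would reach about two months before randomisation. The change should be made, but it does not threaten the validity of the efficacy tests.

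**What to change.** - **Section 2.4:** fit the STI testing GEE to the four 3-month reports (months 3, 6, 9, 12). Use month-1 answers only to complete the 0–3 month interval, by a rule fixed in advance and the same in both arms. The rule must cover both answers: when month 3 is missing, a yes at month 1 settles the interval and a no does not. Report the month-1 30-day percentage by arm descriptively, and do not test it against later surveys. Month 1 can stay in models for outcomes without a recall window, such as PrEP awareness.
- **Section 6.1.2:** state the HIV recall window at each survey. Apply the same rule to the HIV model if the month-1 window is 30 days or reaches before randomisation.
- **Section 10.3.1:** for the testing outcomes, name the four follow-ups as months 3, 6, 9 and 12, and enter baseline testing history as a covariate, not as a time-0 response.

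This is SAP wording, plus confirmation of what the HIV questions ask. In the simulations it costs no power for a constant effect or one starting after month 3. Power for an effect confined to the first month falls, as it should when the target is testing over 12 months. Men who answer month 1 but miss month 3 may contribute little or nothing for that quarter.
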